**KEY STUDY CONTACTS**

[figure not shown]
Insert full details of the key study contacts including the following

Chief Investigator	[name] FRPCH MD Consultant Senior Lecturer Neonatal Medicine [name] [contact] Email: [contact]
Study Co-ordinator	[name] Advanced Neonatal Nurse Practitioner [name] [contact] Email: [contact]
Sponsor	University of Bristol [name]
Key Protocol Contributors	[name] [name] [name] [name]

Study Title	“CoolBonding”: Impact of COVID-19 visiting restrictions on bonding, attachment and mental health of parents of babies cooled for hypoxic-ischaemic encephalopathy: multicentre prospective cohort study.
Internal ref. no.	2019 - 2165
Study Design	A multicentre prospective cohort study investigating maternal bonding, paternal attachment and postnatal depression scores measured using validated questionnaires in parents of babies who underwent therapeutic hypothermia and intensive care for perinatal hypoxic brain injury during the visiting restrictions imposed on parents due to COVID-19 pandemic. After obtaining informed consent, mothers will complete Maternal-Infant Bonding Scale, Edinburgh Postnatal Depression Scale at 5-7 postnatal days and again at 8 weeks postnatally. Fathers or secondary parental figures will complete Edinburgh postnatal depression scale at 5-7 postnatal days and at 8 weeks after birth as well as Paternal Postnatal Attachment Scale at 8 weeks after birth.
Study Participants	Mothers and fathers or secondary parental figures of babies who require therapeutic hypothermia and intensive care for hypoxic-ischaemic encephalopathy.
Planned Sample Size	50 mothers and fathers or secondary parental figures of cooled infants.
Follow-up duration	Up to 12 postnatal weeks
Planned Study Period	01/12/2020 to 01/12/2022
Primary Objective	To investigate the impact of restrictions imposed on parents visiting their babies admitted to intensive care due to COVID-19 pandemic on postnatal depression scores and mother-infant bonding scores at 5-7 days and 8 weeks postpartum in mothers of babies who received cooling therapy.
Secondary Objectives	
 
1. To examine the distribution of postnatal attachment scores between fathers or secondary parental figures and babies who received cooling therapy.
 
2. To investigate the evolution of bonding in mothers and postnatal depression in mothers and fathers or secondary parental figures of babies who received cooling therapy.
 
3. To explore the prevalence of postnatal depression in mothers and fathers or secondary parental figures of cooled babies.
 

Outcomes	
 
1. Mean and confidence intervals of mother-infant bonding score and Edinburgh postnatal depression score (EPDS) in mothers of cooled neonates at 5-7days and 8 weeks postpartum.
 

Secondary	
 
1. Mean and confidence intervals of paternal-postnatal attachment scores at 8 weeks postpartum.
 

	

2. Change in mother-infant bonding scores and postnatal depression scores in mothers and fathers or secondary parental figures between 5-7 days and 8 weeks postpartum.

3. Proportion of parents with postnatal depression at 5-7 days and 8 weeks postpartum.

--	--

**CoolBonding study flowchart**

**ROLE OF STUDY SPONSOR**

Sponsor for this study will be the University of Bristol. Sponsor takes the responsibility for the initiation and management of the study. Sponsor and funder will not have any role in the study design, conduct, data analysis and interpretation and manuscript writing. Sponsor will be involved in the dissemination of the results of the study.

**ROLES AND RESPONSIBILITIES OF STUDY MANAGEMENT COMMITTEES/GROUPS & INDIVIDUALS**

The study will have the investigator group involving two primary investigators ( [name] and [name]) and will liaise with principal investigators at each site, who will oversee the study coordination and conduct at each site. This study was developed with input from the NIHR Southwest Research Design service.

Patient and Public involvement group

Parents of cooled infants form the group. We have discussed about the study design and the outcomes. Parents agree that the outcomes are appropriate to study.

**KEY WORDS: Hypoxic-ischaemic encephalopathy, Therapeutic hypothermia, maternal-infant bonding, paternal infant attachment, Edinburgh postnatal depression score, COVID-19**

## STUDY PROTOCOL

### **“CoolBonding”: Impact of COVID-19 on bonding, attachment and mental health of parents of babies cooled for hypoxic-ischaemic encephalopathy: multicentre prospective cohort study.**

#### **1. BACKGROUND AND RATIONALE**

In the NHS, each year around 2100 infants (3/1000 live births) undergo cooling therapy to reduce death and disability due to brain injury following hypoxic-ischaemic encephalopathy (HIE) occurring secondary to birth asphyxia. Cooling therapy involves cooling the whole body of the newborn baby with encephalopathy within 6 hours of birth using a cooling blanket covering the baby along with intensive care for three days. Cooling therapy is offered in tertiary neonatal intensive care units (NICUs). Babies born in peripheral local neonatal units requiring cooling therapy are transferred to tertiary neonatal units soon after birth. Mothers of these babies are transferred to the cooling centre once they are stable which is typically around 1-2 days after delivery resulting in early separation from their babies. During cooling therapy there is limited physical contact between the babies and their parents for 4 days due to concerns of affecting the process of cooling therapy or intensive care. Further, restrictions imposed on parents visiting their babies admitted in the NICUs during COVID-19 pandemic might worsen the physical and emotional separation between the parents and their babies undergoing cooling therapy.

Parents of babies with HIE experience extreme distress due to the risk of their baby dying (11% of cooled babies die), developing long-term disabilities (22% of cooled babies) or intellectual difficulties (30-40%). Interviews with mothers of cooled infants conducted 4 months to 4 years after giving birth suggested that development of maternal-infant bonding may be affected by the prolonged separation from their baby during cooling therapy, the high-tech NICU environment and the inability to cuddle or hold their baby during cooling therapy. Mothers of cooled babies report poorer bonding compared to control mothers when their babies were 18 months old. We already know that poor maternal-infant bonding can affect the intellectual development of infants. This effect may be exacerbated in cooled babies, already at a higher risk of developmental problems. Direct costs of intellectual disabilities in Europe are estimated at £5.97 billion accruing from health and mental health services utilisation while lifelong welfare support and lost earnings leads to a significant burden to the society and economy.

In addition, postnatal depression may influence the development of maternal-infant bonding. Nearly 21% of mothers of cooled babies report postpartum depression 1 week after delivery. This recent study has shown that mothers of HIE babies may be twice likely to be at risk of having postnatal depression during the first postpartum week, however the prevalence of persistent postnatal depression at 8 weeks postpartum and its influence on maternal-infant bonding in cooled infants, is not known. Fathers or secondary parental figures are important attachment figures for infants. Postnatal depression in fathers or secondary parental figures may influence the development of paternal-infant attachment as well as family dynamics but little attention has been given to father-infant attachment and postnatal mental health of fathers or secondary parental figures of babies with HIE.

For these parents of babies with HIE who are already vulnerable to emotional distress, we do not know whether the visiting restrictions imposed on parents due to COVID-19 impacts the mental health of parents and the bonding and attachment with their infants. There is wide variation across NICUs in allowing parents

to visit their infants who are admitted to intensive care. For example, while St. Michael's hospital NICU in Bristol allows unrestricted access to parents whose babies are admitted to intensive care, Southmead NICU in Bristol only allows 2 hours access for both parents at a pre-booked time and unlimited access is allowed for one parent per baby. Other NICUs have allowed access to one parent per baby. These variations in visiting restrictions might impact the parents' mental health and parent-infant bonding, which are reported to be impacted in parents of infants with HIE in other health care settings.

## RESEARCH QUESTIONS/AIMS

### 2.1 Population

Mothers and/or fathers or secondary parental figures of infants who underwent 72 hours of cooling therapy and intensive care for hypoxic-ischaemic encephalopathy.

#### Inclusion Criteria

1. Parents of babies who have undergone therapeutic hypothermia
2. Up to 7 days postpartum

#### Exclusion Criteria

1. Parents of babies who underwent re-orientation of care during the first 7 days of life
2. Non English-speaking parents which will preclude them from completing questionnaires.

### 2.2 Objectives

#### 2.2.1. Primary objective

To investigate the impact of restrictions imposed on parents visiting their babies admitted to intensive care due to COVID-19 pandemic on maternal postnatal depression scores and mother-infant bonding scores at 5-7 days and 8 weeks postpartum in mothers of babies who received cooling therapy.

#### 2.2.2. Secondary objectives

- To examine the distribution of postnatal attachment scores between fathers or secondary parental figures and babies who received cooling therapy.
- To investigate the evolution of bonding in mothers and postnatal depression in mothers and fathers or secondary parental figures of babies who received cooling therapy.
- To explore the prevalence of postnatal depression in mothers and fathers or secondary parental figures of cooled babies.

### 2.3 Outcomes

### 2.3.1. Primary outcome

Mean and confidence intervals of mother-infant bonding score and Edinburgh Postnatal Depression Score in mothers at 5-7 days and 8 weeks postpartum.

### 2.3.2. Secondary outcomes

- Mean and confidence intervals of paternal-postnatal attachment scores at 8 weeks postpartum.
- Change in mother-infant bonding scores in mothers and postnatal depression scores in mothers and fathers or secondary parental figures between 5-7 days and 8 weeks postpartum.
- Proportion of parents with postnatal depression at 5-7 days and 8 weeks postpartum.

## 3. STUDY DESIGN/METHODS

### 3.1. Study design

Prospective multicentre cohort study

### 3.2. Study setting

#### 3.2.1. Main coordinating centre

Regional Neonatal Intensive Care Unit, St Michael's Hospital, University Hospitals Bristol and Weston NHS Foundation Trust, University of Bristol, Bristol, UK.

## 4. SAMPLE SIZE AND RECRUITMENT

### 4.1 Recruitment

The number of cooled babies cared for in tertiary NICUs in the past years range between 15-20 babies per year. Recruitment will be from up to 6 centres. Doctors or nurses from participating centres will be identified and form a recruitment team under the supervision of the principal investigator. Initial approach to participants regarding the study will always be by a member of their direct care team. Following this, a member of the recruitment team will approach the parents of babies who had received cooling therapy as soon as possible after the clinical team have updated parents of the clinical status of their baby and the treatment plan. They will explain the aims and

content of the study, give the participant information sheet to the parents and give opportunity to ask questions. After sufficient time, parents will have a further opportunity to ask questions. If the parents decide to participate, informed consent will be obtained. Participation will be voluntary. An informed written consent will be obtained from both mother and father or secondary parental figure separately. If only one of the parents consent, they will still be able to participate in the study. In families with same sex parents, we will send the mother-infant bonding questionnaire to the female secondary parent at 8 weeks instead of the paternal postnatal attachment scale.

During COVID-19, most neonatal units are allowing one or both parents to visit their baby at a time to reduce the footfall within the unit and practice adequate physical distancing between people within the unit. The research team will approach whenever parents visit their baby. If the partner is absent when mother is consented, we will obtain mother's permission to approach their partner. We will not approach mothers or fathers who are separated from their babies. They will be approached for the study within 5-7 days of birth when they are with their babies. If either parent has coronavirus infection and not allowed to visit, we will endeavour to approach parents via their telephone number if it is deemed to be appropriate after consulting the clinical team looking after the baby.

If the baby dies after 7 days of age, local team will inform the central research team so that the 8 weeks questionnaires will not be sent.

#### **4.2 Sample size**

We estimated there will be a minimum of 90 eligible sets of parents of cooled infants over 12 months. After excluding 10% due to infant mortality and a further 10% that decline participation or are not recruited due to possible lack of clinical team availability to approach the parents, we anticipate we will recruit 80% of the eligible families of cooled infants (72 families). With a conservative estimate, if a further 20% of the families are lost to follow-up at 8 weeks, we will have 58 families over 12 months. We will aim to recruit 50 families over 18 months to estimate the distribution of bonding, attachment, and postnatal depression scores in parents and associations of centres with different visiting restrictions during COVID-19.

### **5. DATA COLLECTION**

We will use REDCap (a secure web application for managing online surveys and databases) to enable parents to complete questionnaires online as well as entering other data collected during the study.

REDCap will be used to send emails and reminders to parents. For parents not able to access the questionnaires online, we will complete the questionnaires over phone. For participants who are unable to complete the questionnaires over phone, we will post the questionnaires with stamped addressed envelopes for return. The recruiting team at each site will email the consent form to the study coordinator with participants' email address, telephone number and home address via secure NHS email after recruitment. The central study coordinator will register the participant in the REDCap database. Emails containing the link to the questionnaires will be sent to participants at 5-7 days and 8 weeks

postpartum. If the questionnaires are not completed by 8 weeks, an automated email reminder from REDCap will be sent at 9 weeks postpartum. Further reminders may include a text or phone call from the local recruiting team, if the questionnaires are not completed despite the reminder from the REDCap.

### 5.1. Questionnaires

Validated scales of mother infant bonding and paternal postnatal attachment will be used. As postnatal depression can influence parent infant bonding and attachment, postnatal depression will also be measured using a validated questionnaire. Each questionnaire will take up to a maximum of 10 minutes to complete.

#### *Mothers:*

5-7 days following delivery: mother-to-infant bonding scale and Edinburgh postnatal depression scale

8 weeks following delivery: mother-to-infant bonding scale, Edinburgh postnatal depression scale.

#### *Fathers or secondary parental figures:*

5-7 days following delivery: Edinburgh postnatal depression scale

8 weeks: paternal postnatal attachment scale, Edinburgh postnatal depression scale for male secondary parental figure.

8 weeks: mother-to-infant bonding scale, Edinburgh postnatal depression scale for female secondary parental figure.

### 5.2 Other quantitative data

We will collect the demographic data of cooled infants and their parents, perinatal data, and course of neonatal care using Badger.Net (Neonatal Clinical Information System) and from REDCap questionnaires directly entered by the parents. This also includes the impact of COVID-19 such as visiting restrictions, social isolation (childcare/family support), breastfeeding rate.

Demographic data includes parental age, ethnic background, socio economic status, maternal education, family support.

Perinatal Data includes antenatal history, peripartum history, COVID-19 screening, mode of delivery, resuscitation, maternal medication, maternal medical history and birthing hospital.

Neonatal Data includes gestation, sex, severity of HIE, parental participation in care giving, timing of 1st cuddle, mode of feeding, accommodation, visiting restrictions due to COVID-19, length of hospital stay.

## 6. DATA ANALYSIS

Variables that influence the maternal infant bonding and paternal infant attachment including parental age, parity, psychiatric illness, intake of antidepressants, parental education, ethnicity,

socio-economic status and severity of encephalopathy and the implications and degree of COVID-19 restrictions will be summarised for the cohort. The central tendency and dispersion of maternal-infant bonding, paternal-infant attachment scores and postnatal depression scores will be presented as means with 95% confidence intervals for different levels of COVID-19 visiting restrictions by centres. Change in maternal infant bonding and depression scores from week 1 to 8 will be presented as mean or median difference using parametric or non-parametric tests depending on the distribution of the data. We will report the proportion of parents with depression (EPDS  $\geq$  13) at 5-7 days and 8 weeks postpartum. If the visiting restrictions are eased during the study, we will compare the postnatal depression and bonding scores between the restrictions and no-restrictions epochs accounting for the potential confounders.

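### Section 6 compares scores by visiting restriction without accounting for inborn or outborn status, so transfer separation may be mistaken for a restriction effect if the outborn share differs

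*Protocol*

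**What the plan says.** **Who enters.** The Inclusion Criteria take "Parents of babies who have undergone therapeutic hypothermia", up to 7 days postpartum. Neither they nor the Exclusion Criteria refer to place of birth.

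**What transfer does.** Section 1 states: "Babies born in peripheral local neonatal units requiring cooling therapy are transferred to tertiary neonatal units soon after birth". The mothers follow later, "typically around 1-2 days after delivery resulting in early separation from their babies". The same paragraph goes on to say that COVID-19 visiting restrictions might make separation worse.

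**Why separation matters.** Section 1 reports from interviews with mothers that "development of maternal-infant bonding may be affected by the prolonged separation from their baby during cooling therapy".

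**What is collected.** The perinatal data in section 5.2 end with "maternal medication, maternal medical history and birthing hospital".

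**What is analysed.** Section 6 gives its influences on bonding and attachment as "including parental age, parity, psychiatric illness, intake of antidepressants, parental education, ethnicity", followed by "socio-economic status and severity of encephalopathy and the implications and degree of COVID-19 restrictions will be summarised for the cohort". It then presents mean scores with 95% intervals by level of restriction and centre, with no adjustment stated. An adjusted comparison is promised only between epochs, only if restrictions ease, and its confounders are not named.

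**The concern.** The primary objective is the impact of visiting restrictions on maternal bonding and depression scores. Restrictions are expected to act through separation of mother and baby. Transfer of an outborn baby produces separation too, for a reason unrelated to COVID-19, and it falls just before the 5-7 day questionnaire.

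Restriction level is set largely by centre: section 1 contrasts two Bristol units with different rules. The outborn share is plausibly a centre characteristic as well, because it depends on how many babies each unit receives from local units. With at most six centres (section 4.1), balance of outborn families across restriction levels cannot be assumed. Where they are unbalanced, the unadjusted difference between levels mixes the two sources of separation.

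**Working it through.** **1. The plan's own figures.** The plan gives no figure on this point. Its only computed figures, in section 4.2, reproduce: 90 × (1 − 0.10 − 0.10) = 72 families recruited, and 72 × (1 − 0.20) = 57.6, rounded to 58, at 8 weeks. The target is 50 families. No SD, effect size or outborn share is given.

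**2. Form of the bias.** If restrictions had no effect at all, the unadjusted difference in mean score between two restriction levels would be

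bias = (difference in outborn share between levels) × (effect of transfer separation on the score).

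Both factors are missing from the documents, so the values below are assumptions. Bias in SD units:

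| Assumed effect of transfer | Share difference 0 | 20 points | 40 points | 60 points |
|---|---|---|---|---|
| 0.3 SD | 0 | 0.06 | 0.12 | 0.18 |
| 0.5 SD | 0 | 0.10 | 0.20 | 0.30 |
| 0.8 SD | 0 | 0.16 | 0.32 | 0.48 |

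On the Edinburgh scale, an assumed transfer effect of 2 to 4 points with share differences of 20 to 40 percentage points gives 2 × 0.20 = 0.4 to 4 × 0.40 = 1.6 points. With no share difference it is again 0.

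**3. Against the study's precision.** Assume the 50 mothers split 25 v 25 between two restriction levels. The SE of the difference is √(2/25) = 0.28 SD, and the 95% half-width is 1.96 × 0.283 = 0.55 SD. The chance that the interval for the difference excludes zero when restrictions have no effect is 1 − Φ(1.96 − b/SE) + Φ(−1.96 − b/SE), where b is the bias:

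| Bias b | Chance |
|---|---|
| 0 | 5.0% |
| 0.10 SD | 6.4% |
| 0.20 SD | 10.9% |
| 0.48 SD | 39.6% |

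**4. What adjustment costs.** With equal groups and an average outborn share of one half (assumed), the correlation between restriction level and outborn status equals the share difference d. The SE then grows by 1/√(1 − d²): 1.02 at 20 points, 1.09 at 40 points, 1.25 at 60 points. This is before any gain from lower residual variance if transfer does affect the score.

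**5. Why not a full split.** Fifty families over six centres is 50/6 = 8.3 per centre. Halved by birthplace, that is about 4 per cell. Two restriction levels by birthplace gives 50/4 = 12.5 per cell.

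**The case against.** The strongest objection is that a detailed covariate list belongs in a statistical analysis plan, which is not shown here. Section 6 already promises to account for confounders in the epoch comparison, without limiting the set, and the variable needed is collected. This stands in part: nothing in section 6 rules place of birth out. But that promise covers only the epoch comparison, and only if restrictions ease. The presentation by restriction level and centre has no adjustment stated, and it is the comparison that will exist whatever happens to the rules.

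Three stronger readings are tempting, and the documents do not support them.

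- A reader might infer that transfer separation will be reported as a restriction effect. That requires unequal outborn shares, and the documents give no shares.
- A reader might take the section 6 list as an adjustment set with one covariate missing. The list is open-ended, and its variables are to be summarised, not adjusted for. Adding place of birth to it would therefore not correct the comparison.
- A reader might take transfer to be the only non-COVID limit on contact. Section 1 also describes about four days of limited physical contact for cooled babies in general. Transfer stands out because it differs between families.

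It is also fair to say that section 1 ties bonding to separation during cooling, not to transfer specifically, and does not tie separation to depression scores. The case is therefore firmer for bonding than for the Edinburgh score. Finally, biases of 0.10 to 0.20 SD are well inside a half-width of 0.55 SD.

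**Conclusion.** The point holds in a limited form. The protocol describes a one-to-two-day separation from transfer on the same pathway as the exposure, and it collects the variable that identifies it. Its comparison by restriction level nevertheless makes no use of that variable. If the outborn share differs between restriction levels or epochs, transfer separation may be read as a restriction effect.

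The size cannot be derived from the documents. Over the assumed ranges it runs from exactly 0 to 0.48 SD. With a mid-range effect of 0.5 SD and differences of 20 to 40 points it is 0.10 to 0.20 SD, and the error rate rises from 5% to 6.4% or 10.9% under an assumed 25 v 25 split. This is a worthwhile and inexpensive improvement. It is not a flaw that invalidates the study.

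**What to change.** Amend section 6 as follows.

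1. Derive inborn/outborn status by comparing birthing hospital with the cooling centre.
2. Report the outborn share at each restriction level and in each epoch, so that a reader can see whether imbalance exists.
3. Give the difference in mean bonding and Edinburgh scores between restriction levels adjusted for this status. Alternatively, show the means by restriction level separately for inborn and outborn families. Do not split by centre and birthplace together.
4. Name the status in the confounder set for the epoch comparison.

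Place of birth is fixed before the cooling centre's visiting rule can act, so adjusting for it does not remove any of the restriction effect. That is not true of timing of first cuddle or parental participation in care, which section 5.2 also collects and which may lie on the pathway. Adjustment for place of birth will not remove other differences between centres, and the text should say so.

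The cost is a change of analysis wording, with no new data. Intervals widen slightly (2% to 9% for share differences of 20 to 40 points under the assumptions above), and a split table would have small cells with about 50 families.

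### If visiting restrictions are not eased, the primary objective (their impact on maternal scores) has no planned effect estimate, only a separate mean and interval for each restriction level

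*Protocol*

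**What the plan says.** Section 2.2.1 (Primary objective) is comparative: "To investigate the impact of restrictions imposed on parents visiting their babies admitted to intensive care due to COVID-19 pandemic on maternal postnatal depression scores". Bonding is treated in the same way, and both scales are taken at two time points. Section 4.2 (Sample size) adds the aim of estimating "associations of centres with different visiting restrictions during COVID-19". Section 1 (Background and rationale) explains why a comparison is possible. Units differ in how much parental access they allow, and at least three patterns are described, from unrestricted access to one parent per baby.

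The primary outcome in section 2.3.1 is descriptive: "Mean and confidence intervals of mother-infant bonding score and Edinburgh Postnatal Depression Score in mothers at 5-7 days and 8 weeks postpartum". Section 6 (Data analysis) carries this through. The scores "will be presented as means with 95% confidence intervals for different levels of COVID-19 visiting restrictions by centres".

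Section 6 plans two contrasts. One is within-parent change from week 1 to week 8. The other is between periods: "If the visiting restrictions are eased during the study, we will compare the postnatal depression and bonding scores between the restrictions and no-restrictions epochs". The protocol says that this second contrast will be made "accounting for the potential confounders".

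**The concern.** An impact, or an association with restriction level, is a difference between levels. The plan contains that difference only in the epoch comparison, which depends on an event outside the study's control. The exposure variation that the study can expect from the outset, between centres with different access rules, is summarised one level at a time, with no estimated difference, no interval for a difference and no model.

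If restrictions stay in place throughout recruitment, the study could follow its protocol exactly and still report no effect estimate for its main question. Readers would be left to compare adjacent intervals by eye, which is a much stricter test than it looks.

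**Working it through.** **The plan's own figures.** Section 4.2 gives a feasibility count: 90 eligible × 0.80 = 72 recruited, and 72 × 0.80 = 57.6, rounded to 58 followed to 8 weeks, against a target of 50 families. These reproduce. The section gives no SD, effect size, power or precision target, so there is no planned precision for a difference to check.

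**What is asked against what is delivered.**

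| Place | Content | Difference between levels? |
|---|---|---|
| 2.2.1 | Impact of restrictions on two maternal scales at two times | Required by the question |
| 4.2 | Associations with different restrictions | Required by the aim |
| 2.3.1 | Means and CIs of those scales | No |
| 6, by restriction level | One mean and 95% CI per level, by centre | No |
| 6, epochs | Restrictions v no restrictions, adjusted | Yes, but only if restrictions are eased |

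The epoch comparison also contrasts two periods, not the graded access rules across units. Section 1 describes one unit that already allowed unrestricted access. A unit like that would show little change at easing, so its contrast with stricter units would not be captured by period alone.

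**How poor a substitute separate intervals are.** Assumptions, since the protocol gives none: two restriction levels, equal SDs, independent mothers, normal theory, effects in SD units, and the 50 families each contributing a mother.

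- Two 95% intervals fail to overlap when |difference| > 1.96 × (SE1 + SE2).
- The 95% interval of the difference excludes zero when |difference| > 1.96 × √(SE1² + SE2²).

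With 25 and 25, each SE is 1/√25 = 0.20 SD:

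- Non-overlap: 1.96 × 0.40 = 0.784 SD.
- Interval of the difference: 1.96 × √0.08 = 0.554 SD.
- Ratio: 0.784 / 0.554 = 1.41.

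| Split of 50 | Non-overlap needs | CI of difference needs | Ratio |
|---|---|---|---|
| 25 / 25 | 0.784 SD | 0.554 SD | 1.41 |
| 17 / 33 | 0.817 SD | 0.585 SD | 1.40 |
| 10 / 40 | 0.930 SD | 0.693 SD | 1.34 |

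If someone did read the 25/25 case by overlap, a true difference of 0.8 SD (difference / SE = 0.8 / 0.283 = 2.83) would be seen with probability Φ(2.83 − 2.77) ≈ 52%, against Φ(2.83 − 1.96) ≈ 81% with the interval of the difference. A simulation using t-based intervals gives 48% against 79%.

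The third column is also the half-width of the interval that the plan would report if it estimated the difference: about ±0.55 to ±0.69 SD before any allowance for centre.

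**The case against.** Four points can be made for the plan.

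*A comparison is planned.* A reader might infer from the per-level means that the protocol never compares restriction levels. That goes too far. The last sentence of section 6 commits to an adjusted comparison of both scales between epochs. What stands is that it is conditional and concerns periods.

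*No overlap rule exists.* A reader might infer that impact will be judged by whether intervals overlap. The protocol states no such rule, and a crude unadjusted difference could be worked out from the published means and intervals. The overlap figures therefore show a risk of misreading; they do not measure a loss caused by a stated analysis. The 1.41 ratio is also the most unfavourable case, reached only with equal standard errors.

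*The model belongs in the statistical analysis plan.* Model form and interval method can properly be left there, and that document, if it exists, is not to hand. But the protocol is not silent here. It fixes the primary outcome as separate means, and an analysis plan that followed it would inherit the mismatch with the objective.

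*The depression proportion.* Section 6 says "We will report the proportion of parents with depression" and mentions neither an interval nor a split by restriction level, which a reader might count as part of the same fault. It is not. Prevalence is a secondary, exploratory objective that is not defined by restriction level, and an interval for it is a reporting detail.

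**Conclusion.** The point holds as a mismatch between the objective and the fixed primary read-out. Without easing, the primary question has no planned contrast. With easing, it has one between periods, but still none between the access levels that motivate the study. The mismatch itself rests on the text alone and needs no assumption.

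Its size can only be illustrated: 0.78 SD against 0.55 SD with two groups of 25, on assumed equal SDs, two levels and independent mothers. Splitting the families over more than two levels, or allowing for clustering by centre, would reduce power under either reading. The change should be made, because it is cheap and lets the study answer its own question. Nothing here implies that the per-level means are wrong as description.

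**What to change.** In sections 2.3.1 and 6, and in the matching entry of the study summary, state without condition that for each maternal scale at each time point the difference in mean score between restriction levels will be estimated with its 95% CI from one model containing all mothers. The model should:

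- adjust for the confounders that section 6 already lists (parental age, parity, psychiatric illness, antidepressant use, education, ethnicity, socio-economic status, severity of encephalopathy);
- allow for centre, because restriction level is largely set by centre. Where a centre keeps one level throughout, level and centre cannot be fully separated, and the result should be reported as an association, not an effect of the restrictions.

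Keep the per-level means and intervals as description, and keep the epoch comparison as an addition if restrictions are eased.

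Cost: wording, and regression models on data that sections 5.2 and 6 already plan to collect. No extra families or questionnaires are needed. The downside is that with about 50 families, up to 6 centres and eight listed covariates, the interval will be wide, probably wider than the ±0.55 SD of the simple two-group case. That width is the honest statement of what the study can show.
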